## 5. METHODS AND PROCEDURES

### 5.1. Study Procedures

- Study personnel will complete the electronic **Screening Log** to monitor all subjects approached for participation in this study, the outcome of the assent/consent process (declined or enrolled), and reason for declining participation.
- Study Personnel will complete the **Eligibility Checklist** for each pair of subjects who provide assent and consent for participation in this study.
- **Washout Period:** Patients who are already taking tacrolimus (i.e., Protopic), crisaborole (i.e., Eucrisa), or any steroid- sparring medication for atopic dermatitis are eligible for the study if he/she agrees to discontinuation of the medication for two weeks (i.e., 14 days) prior to starting study procedures. If the patient agrees to the two week "washout period", assent and informed consent can be obtained during that clinic visit. A study visit will be scheduled for the patient and caregiver at a convenient time at least two weeks (i.e., 14

days) from the day of assent/consent. After the two week “washout period”, the subject will return to clinic for the baseline study visit and be randomized to tacrolimus 0.03% or crisaborole. The subject will either be given a tube of tacrolimus 0.03% or crisaborole. All study procedures will continue as described below starting with the **ASPIRE On-study Form**.

- Assent and informed consent are obtained from each subject, without coercion, prior start of any study procedures. Assent Form 1 will be used for subjects ages 8 to 12 years and Assent Form 2 will be used for subjects ages 13 to 15 years. Informed consent will be completed by the parent/adult caregiver. The caregiver subject will provide their name, mailing address, and signature on the **Study Reimbursement Form**. Each subject (child and adult) will complete a W9 form for study reimbursement.
- Study personnel will notify the caregiver that they will be contacted by phone for reminders about upcoming study appointments and screening for any adverse reactions. Study personnel will ask if leaving a voicemail message is okay in case a call is missed. This information will be kept in a password-protected excel file **Call Log** located in the study folder on the Dermatology CTU’s University sharedrive. Study personnel will only have access to this study folder and the excel file.

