- Study personnel will add appropriate subject information and study progress to the **Comprehensive Study Log**, as required by RSRB. This log is a password-protected excel file located in the study folder on the Dermatology CTU’s University sharedrive. Study personnel will only have access to this study folder and excel file.
- Subjects will be on study for at least 12 weeks. Subjects will be assessed at three different time points (Baseline, 6 Weeks, and 12 Weeks). Each assessment will be performed in the dermatology clinic and take approximately 30 minutes or less
- Pediatric subjects will be randomized 1:1 to one of two topical treatments: crisaborole or tacrolimus 0.03%. Both of these topical treatments are standard care for mild to moderate atopic dermatitis. Study personnel will obtain randomization in REDCap. After randomization, the treating dermatologist (i.e., [REDACTED]) will prescribe crisaborole or tacrolimus 0.03% to the pediatric subject for treatment of atopic dermatitis. Study personnel will dispense a tube of tacrolimus 0.03% or crisaborole to the subject based on randomization. The topical treatments will be applied to all affected areas twice daily for at least 12 weeks on this study. Additional tubes of tacrolimus 0.03% or crisaborole will be dispensed to the subject if needed to complete the 12 week treatment and assessment period. At the completion of the study, the treating dermatologist may continue or change the prescribed treatment for atopic dermatitis.
- Study personnel will complete the **ASPIRE On-Study Form** in REDCap. This form collects demographic information on both the pediatric subject and caregiver subject. Additionally, the form collects treatment information related to atopic dermatitis, all current medications, and medical history for the pediatric subject. This form will be completed after assent and consent are obtained.

- **Baseline Assessment:**
  - *Study personnel:* Trained study personnel (MD/NP) will perform Eczema Area & Severity Index (EASI), Investigator Static Global Assessment (ISGA), and Percentage Body Surface Area (%BSA) for the severity of atopic dermatitis. Study personnel will also weigh the tube of crisaborole and tacrolimus 0.03% prior to distribution to the subject. Study personnel will have an average weight for tube of tacrolimus prescribed. Study personnel will enter EASI, ISGA, and tube weight into the electronic **Assessment Form (Baseline)** in REDCap.

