#### **5.5. Blinding Methods**

This is an open-label study and is not blinded.

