### 13. SCHEDULE OF EVENTS AND DATA COLLECTION

Study Procedures	Screening	Baseline Assessment	3 Week	6 Week Assessment	9 Week	12 Week Assessment
Eligibility Checklist 	X	X				
Assent and Informed Consent 	X	X				

Randomization	X	X					
Screening Log		X					
Comprehensive Study Log	Completed as needed throughout the study.						
Reimbursement Form/W9	X	X					
ASPIRE On-Study Log	X	X					
Drug Accountability Record		X					
Assessment Form:							
ISGA		X		X		X	
EASI		X		X		X	
%BSA		X		X		X	
AD Patient PROs:							
PROMIS Itch		X		X		X	
PROMIS Pain Interference		X		X		X	
PROMIS Anxiety		X		X		X	
PROMIS Depression		X		X		X	
CDLQI		X		X		X	
CSHQ		X		X		X	
Caregiver PROs:							
CBI		X		X		X	
FDLQI		X		X		X	
AD Flare Medication Form		Completed as necessary during study.					
AE Monitoring			X	X	X	X	
Call Log			X	X	X	X	
AE Source Doc	Completed as necessary during study.						
Pfizer SAE Form/Cover Sheet	Completed as necessary during study.						
Withdrawal Form	Completed as necessary during study.						
Pediatric Subject							
Reimbursement Form/\$10 Gift Card		X 		X 		X 	
Request For Payment (RFP) for Caregiver Reimbursement		Completed at completion of study procedures and/or subject participation					

Eligibility checklist can be completed before or at the Baseline Assessment.

Assent and consent can be obtained prior to Baseline Assessment.

Completed after assent and consent are obtained and can be same visit as assent and consent.

Pediatric subject reimbursed with gift card at completion of study visit. Subjects must complete and sign the Pediatric Reimbursement Form at each visit to receive the \$10 gift card

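### The plan does not require baseline questionnaires and severity scores to be finished before the open-label assignment is known, and for washout patients it puts randomisation and the tube first

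*Combined protocol and SAP*

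**What the plan says.** **Washout patients.** The Washout Period item of Section 5.1 gives a sequence. After the two weeks off medication, "the subject will return to clinic for the baseline study visit and be randomized to tacrolimus 0.03% or crisaborole". Next, "The subject will either be given a tube of tacrolimus 0.03% or crisaborole". Then: "All study procedures will continue as described below starting with the" ASPIRE On-Study Form. In the list that follows, the Baseline Assessment comes after that form.

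**Other patients.** Section 5.1 lists randomisation, prescription and dispensing in one item ("Study personnel will dispense a tube of tacrolimus 0.03% or crisaborole to the subject based on randomization"), then the On-Study Form, then the Baseline Assessment with EASI, ISGA, %BSA and the questionnaires. The Baseline Assessment item itself adds: "Study personnel will also weigh the tube of crisaborole and tacrolimus 0.03% prior to distribution to the subject". Section 5.2 says the crisaborole tube is handed out at the Baseline Assessment; its tacrolimus paragraph gives no time.

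**Schedule.** Section 13 marks randomisation under both Screening and Baseline. The footnote attached to it reads: "Completed after assent and consent are obtained and can be same visit as assent and consent". Another footnote lets assent and consent be obtained ahead of the Baseline Assessment.

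**Blinding.** Section 5.5: "This is an open-label study and is not blinded". Section 5.1 lets a parent or guardian help the child with the self-report measures.

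**The concern.** The baseline is half of each primary outcome. Section 1.4 defines these as the 12-week change in PROMIS Itch and PROMIS Pain Interference, and Section 11.2 compares the arms by t-tests on the changes. A child or parent who already knows the arm may report itch and pain differently. A clinician who knows it may score EASI or %BSA differently, and those scores feed the planned correlations.

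Expectations are unlikely to be equal in the two arms. Section 1.2 reports that many clinicians think crisaborole the more effective product, and the investigators expect it to be superior. Section 11.1 rests the superiority claim on the patient-reported outcomes and not on EASI, so the self-reported baseline carries real weight. A baseline collected after the assignment is known cannot be repaired in the analysis.

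**Working it through.** The plan gives no figure on this point, so there is none to reproduce. The first step is to compare the texts.

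| Text | What it fixes |
|---|---|
| 5.1, Washout Period | Randomise on return, tube, On-Study Form, later the Baseline Assessment: an explicit order |
| 5.1, general items | Same order, but only by position in the list |
| 5.1, Baseline Assessment item | Tube weighed before hand-over; order against questionnaires not stated |
| 5.2, crisaborole | Hand-over at the baseline visit; order within it not stated |
| 5.1, 6 Week Assessment item | Treatment starts after the Baseline Assessment |
| 13, marks and footnotes | Randomisation allowed once consent is given, including at the consent visit |

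Two things follow. Section 13 and the washout text disagree: for a washout patient the consent visit is at least 14 days before baseline, whereas Section 5.1 randomises on return. And no text places the baseline measures before the assignment is obtained or disclosed, or provides an assessor unaware of it.

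The second step is the possible size. Let b be the shift in one arm's mean baseline caused by knowing the arm, p the fraction of it still present at week 12, and β the within-arm slope of week-12 score on baseline.

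- Bias in the change-score contrast: p·b − b = −(1 − p)·b.
- Bias in a baseline-adjusted ANCOVA: p·b − β·b = (p − β)·b.

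*Baseline only (p = 0), b assumed 1, 2 or 3 points.* The change contrast is off by 1, 2 or 3 points. Against the 5-point change in Section 1.4 this is 1/5 = 20%, 2/5 = 40%, 3/5 = 60%. ANCOVA keeps β·b: at β = 0.5 this is 0.5, 1.0 or 1.5 points; over β from 0.3 to 0.7 it runs from 0.3 × 1 = 0.3 to 0.7 × 3 = 2.1 points.

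*Equal persistence (p = 1).* The change contrast is off by 0. ANCOVA would then carry (1 − β)·b.

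*Type I error when p = 0.* Inputs from Section 11.1: SD 10, 20 per arm, two-sided 0.05. Assumed: SD 10 at both visits, baseline to week-12 correlation r of 0.3 to 0.7 (so β = r), normal approximation. For r = 0.5 and b = 2:

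- Change score: SE = 10 × √(2 × 0.5) × √(2/20) = 3.16; 2/3.16 = 0.632; Φ(0.632 − 1.96) + Φ(−0.632 − 1.96) = 0.092 + 0.005 = 0.097.
- ANCOVA: SE = 10 × √(1 − 0.25) × √(2/20) = 2.74; 1.0/2.74 = 0.365; Φ(0.365 − 1.96) + Φ(−0.365 − 1.96) = 0.055 + 0.010 = 0.065.

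| Assumed shift b | Change-score t-test, r 0.3 to 0.7 | ANCOVA, r 0.3 to 0.7 |
|---|---|---|
| 1 | 0.058 to 0.069 | 0.051 to 0.061 |
| 2 | 0.083 to 0.129 | 0.055 to 0.095 |
| 3 | 0.126 to 0.232 | 0.060 to 0.153 |

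Children under 5 complete no self-report measures (Section 5.1), so fewer than 20 per arm may contribute. The bias in points would be the same, but the type I error would be nearer 0.05.

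**The case against.** The best defence is that the plan describes a single baseline visit and simply does not spell out the order within it. Much of this stands.

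- **Hand-over first for everyone.** A reader might infer this from the list in Section 5.1. The documents do not support it outside the washout route. The list is not strictly chronological (consent comes after the eligibility checklist and the washout item), and the Baseline Assessment item and Section 5.2 put hand-over inside the visit without ordering it. But knowing the arm needs only the assignment, not the tube, and nothing delays its disclosure.
- **Randomisation before washout.** A reader might combine the Section 13 footnote with the 14-day interval and conclude that losses during washout become post-randomisation losses. Section 5.1 expressly randomises on return. What stands is a contradiction to reconcile, not a planned practice.
- **Drug effect on the baseline.** Excluded: treatment starts after the Baseline Assessment.
- **Eligibility after washout.** Section 13 says "Eligibility checklist can be completed before or at the Baseline Assessment", so a reader might ask whether severity is reconfirmed. That is a separate question about the population and does not bear on knowledge of the arm.
- **The size is assumed.** Correct. The documents support neither the 1 to 3 points nor a direction, and Section 11.2 names no ANCOVA covariate. Both arms receive free, active, standard-care ointments, so expectations may differ little.
- **Reports are open-label throughout.** Also correct. A reporting shift that lasted equally to week 12 would cancel in the change score. That would be an accidental offset between two biased measurements, not a safeguard.

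**Conclusion.** The point holds as a gap in the stated order, with a possible bias of unknown size. It is explicit for washout patients, suggested by the list order for others, and made worse by a schedule that conflicts with Section 5.1. Confidence is high that no text puts the baseline measures before the assignment, moderate that hand-over comes first outside the washout route, and low on magnitude.

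If the shift affects one arm's baseline only, the change-score contrast is off by the full shift, and a baseline-adjusted ANCOVA reduces this to slope times shift without removing it. The 1 to 3 points, the correlations and the absence of persistence are all assumptions. A reader might infer that the baseline will be biased; the documents show only that it could be. EASI, ISGA and %BSA are not primary outcomes, so for them the exposure is limited to secondary uses such as the planned correlations.

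This should be fixed because it is an avoidable exposure of the primary outcome and the remedy is almost free.

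**What to change.** Reconcile Sections 5.1 (washout item, general items, Baseline Assessment), 5.2 and 13 to one order:

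1. Consent and assent.
2. Washout, if needed.
3. Baseline questionnaires and EASI, ISGA and %BSA completed and saved.
4. REDCap randomisation, released only once step 3 is saved.
5. Dispensing.

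Remove the Screening mark for randomisation in Section 13, and give that row its own footnote, since the present one is shared with the reimbursement and On-Study rows. Patients without washout can still do all five steps in one visit.

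One practical detail: Section 5.1 enters the tube weight on the same baseline form as the severity scores. The release should depend on the scores and questionnaires, with the tube weight added after assignment.

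The cost is a reordered visit and a form dependency in REDCap, which already holds the randomisation and the baseline data. No extra visit, staff or patients are needed. The change removes knowledge of the arm from the baseline only; it does nothing about open-label reporting at weeks 6 and 12, which remains a limitation to acknowledge.

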  - *Pediatric Subjects:* Pediatric subjects ( $\geq 5$  years) will complete five self-report outcome measures (**PROMIS® Itch, PROMIS® Pain Interference, Children's Dermatology Life Quality Index (CDLQI), PROMIS® Anxiety, PROMIS® Depression**) on an iPad. All self-report measures can be completed with the assistance of their parent or guardian. All five self-report outcome measures can be completed in 20 minutes or less. Pediatric subjects  $< 5$  years will not complete any self-report measures on the iPad.
  - *Caregiver Subjects:* All caregivers will complete one self-report questionnaire about their child's sleep habits (**Children's Sleep Habits Questionnaire (CSHQ)**) and two self-report measures for caregiver burden (**Caregiver Burden Inventory (CBI)**) and quality of life (**Family Dermatology Life Quality Index (FDLQI)**) on an iPad. All self-report measures can be completed in 5 minutes.
- Pediatric subjects will complete a Pediatric Subject Reimbursement Form at the end of the Baseline Assessment. The pediatric subject will print their name, address, sign and date the form. The adult caregiver may help the child complete the form if he/she has difficulty writing. Pediatric subject  $\geq 5$  years must sign the form. Study personnel will give the pediatric subject a \$10 gift card after for the completion of this form for completion of the Baseline Assessment. For pediatric subjects  $< 5$  years, the adult caregiver will complete and sign the form. Study personnel will give the adult caregiver subject a \$10 gift card after for the completion of this form for completion of the Baseline Assessment.
- Study personnel will call the caregiver by phone during the Week 3 of treatment for adverse event monitoring of their child who is participating and on topical treatment. Study personnel will ask: 1) Has your child been able to use the topical treatment without any problems?; 2) Has your child experienced any burning from the topical treatment?; and 3) Has your child experienced any side effects or adverse reactions while using the topical treatment?. Study personnel will document the phone call in the Call Log. Adverse events will be documented on AE source doc.
- Study personnel will call the caregiver by phone at least 48 hours prior to the 6 Week Assessment to remind he/she of their upcoming appointment and to bring their tube of topical treatment with them to the appointment. Study personnel will also monitor for

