## **9. SAFETY AND REPORTABLE EVENTS**

### **9.1. Adverse Event Monitoring**

This study does not involve interventional or clinical endpoints for individual patients. The treatment prescribed to patients in the study is part of standard care for mild to moderate atopic dermatitis in children and adolescents. Although the patients will receive one of two topical treatments for atopic dermatitis, the primary outcome of the study is not clinical response to treatment. Crisaborole and tacrolimus 0.03% ointments are both FDA-approved for atopic dermatitis and applied twice daily to affected areas of skin. Although this is an open-label, cross-sectional study, safety information may be identified during the course of data collection. Adverse event monitoring will be performed by phone at four different times during the study (i.e., Week 3, Week 6, Week 9, and Week 12). Any AEs will be documented on the AE Source Doc. Any safety information for an individual patient that is volunteered by a study subject during the course of this research must be reported as described below:

All adverse event, whether observed by the Investigator, elicited from, or volunteered by the subject, should be documented. Each adverse event will be recorded on the electronic AE Source Doc. This form will record the will include a brief description of the experience, the date of onset, the date of resolution, the duration and type of experience, the severity, contributing factors, and any actions taken. This description will be in the summary not during a subject's regularly scheduled clinic appointment.

**Adverse event (AE):** is any untoward medical occurrence in a subject administered study drug (active drug or placebo), and which does not necessarily have a causal relationship with this treatment. An adverse event can be any unfavorable and unintended sign (including abnormal laboratory test results), symptom, or disease temporally associated with the use of the study drug, whether or not considered related to the study drug. The relationship of each adverse event to the study drug (active drug or placebo) must be recorded as one of the choices on the scale described below.

**Attribution:** An assessment of the relationship between the adverse event and the protocol treatment, using the following categories.

ATTRIBUTION	DESCRIPTION
Unrelated	The AE is clearly NOT related to treatment.
Unlikely	The AE is doubtfully related to treatment.

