**Research staff (i.e., PI, Co-investigators, or study coordinator):** Will also conduct continuous review of data and subject safety. The review will include for each treatment arm/dose level: the number of subjects, adverse reactions, and responses observed. The Investigator will submit summaries of this data to the Data Safety Monitoring Committee for review as required in the study's protocol review committee approval letter.

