## **10. RISK/BENEFIT ASSESSMENT**

### **10.1. Potential Risks**

The proposed study is a low risk clinical trial. Subjects (patients & caregivers) will be completing self-report questionnaires at three different regularly scheduled clinic visits. The two topical treatments in the study are FDA-approved and standard care for  $\leq$ moderate atopic dermatitis. Crisaborole is approved for use in ages 2 years and older. Known side effects to crisaborole include pain at the site of application. Tacrolimus 0.03% is approved for use in ages 2 to 15 years. Known side effects to tacrolimus 0.03% include burning sensation, stinging, soreness, or pruritus at the site of application. These localized symptoms may occur during the first few days of use and subside as atopic dermatitis lesions improve. Subjects using tacrolimus should limit sun exposure and should not use ultraviolet light therapy, sun lamps, or tanning beds. Tacrolimus-treated skin should not be covered with bandages, dressings, or wraps. Contact of tacrolimus with eyes or mouth should be avoided. Unexpected side effects, such as allergic reactions, may occur and are unpredictable. This reaction may be mild, such as a skin rash, or you may have more severe symptoms like swelling of the throat, low blood pressure, and shortness of breath. If any of these unexpected side effects occur, subjects will be advised to stop use of their intervention immediately. Subjects will be informed about any additional potential risks if they are discovered. Furthermore, while we make every effort to keep all data and study information private, this cannot be guaranteed. All data will be de-identified and stored in a locked file in a locked office. All appropriate procedures will be taken to maintain subject privacy and data collected during this study.

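### The safety calls name only burning, and only in two of four calls, so local reactions to the two ointments may be elicited unevenly, and nothing is solicited before Week 3

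*Combined protocol and SAP*

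**What the plan says.** **Calls.** Section 9.1 has adverse event monitoring "performed by phone at four different times during the study (i.e., Week 3, Week 6, Week 9, and Week 12", and the schedule in section 13 shows no adverse event monitoring before the 3 Week column. Section 5.1 gives the first: "Study personnel will call the caregiver by phone during the Week 3 of treatment for adverse event monitoring".

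**Script.** The Week 3 call and the call before the 6 Week visit each put three questions: one on trouble-free use, one on burning ("2) Has your child experienced any burning from the topical treatment"), and one open question on any side effect. The Week 9 call and the reminder call after it keep the two general questions and omit the burning question.

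**Known reactions.** Section 10.1 states for one drug: "Known side effects to crisaborole include pain at the site of application". For the other it states: "Known side effects to tacrolimus 0.03% include burning sensation, stinging, soreness, or pruritus at the site of application". The next sentence reads: "These localized symptoms may occur during the first few days of use and subside as atopic dermatitis lesions improve".

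**Use of the data.** Section 9.3 describes a continuing review by research staff, with summaries sent to the Data Safety Monitoring Committee: "The review will include for each treatment arm/dose level: the number of subjects, adverse reactions, and responses observed".

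**Start of monitoring.** Section 9.2 says monitoring begins when topical treatment begins, and that complaints volunteered by the subject are recorded.

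**The concern.** A script that names one symptom beside a general question treats that symptom differently from the rest. Here the named symptom is on one drug's list and not on the other's. Section 5.5 says the trial is not blinded, so the caregiver knows which ointment is being described. If naming a symptom raises the chance that it is mentioned, a tacrolimus-listed reaction gets help that the crisaborole-listed reaction does not. The burning question also disappears halfway through, so counts from the first two calls and the last two are not collected in the same way.

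Timing is the second issue. Reactions that may come and go in the first days of use are first asked about in Week 3.

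At stake is the tolerability description by arm. That matters because section 2.1 says the study will show whether crisaborole is the better overall treatment, and a reader will set the two adverse-reaction lists beside each other. Application-site pain and itching also lie close to the two primary outcomes, pain interference and itch, yet neither is asked about by name as a reaction to the ointment.

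**Working it through.** The plan gives no figure to reproduce on this point. The check sets the script against the reaction list, then counts days.

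**1. Prompts by call (section 5.1)**

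| Call | General questions | Symptom named |
|---|---|---|
| Week 3 | 2 | Burning |
| Before the 6 Week visit | 2 | Burning |
| Week 9 | 2 | None |
| Last reminder call | 2 | None |

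The text labels the last call as preceding the 6 Week Assessment. It stands between the Week 9 call and the 12 Week Assessment, so I read it as the 12 Week reminder.

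**2. Listed reactions (section 10.1) against prompts**

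| Reaction | Listed for | Named in |
|---|---|---|
| Application-site pain | Crisaborole | 0 of 4 calls |
| Burning | Tacrolimus | 2 of 4 calls |
| Stinging | Tacrolimus | 0 of 4 calls |
| Soreness | Tacrolimus | 0 of 4 calls |
| Pruritus | Tacrolimus | 0 of 4 calls |

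Named at any time: 1 of 4 tacrolimus reactions, 0 of 1 crisaborole reactions, 1 of 5 overall.

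**3. Delay to the first solicited contact**

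- Assumption: Week 3 is Days 15 to 21, so 14 to 20 full days pass first.
- Treatment period: 12 weeks × 7 = 84 days.
- Share elapsed: 14/84 = 17% to 20/84 = 24%.
- Twice-daily applications by then: 14 × 2 = 28 to 20 × 2 = 40.

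The first few days that section 10.1 mentions lie wholly inside this interval. The Week 3 questions set no look-back limit, so they reach those days, but by recall of roughly two to three weeks.

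**4. Section 9.2 against the schedule.** Section 9.2 starts monitoring with treatment. Sections 5.1, 9.1 and 13 schedule no contact before Week 3 that would do so. Until then capture is passive.

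**5. Dates.** Section 9.1 says the AE Source Doc records onset, resolution and duration. The fields listed for that form in section 5.3 include onset but no resolution date. For a reaction expected to fade, the missing field is the one needed to describe it.

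**The case against.** The case on the other side is substantial.

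- **The script is the same in both arms.** Every call also carries two general questions, and application-site pain would be a natural answer to either. Section 10.1 introduces each list as what the known effects include, so neither need be complete and burning is not shown to belong to tacrolimus alone. A reader might infer that reactions are captured unequally. The documents support only a risk of unequal elicitation.
- **The timing sentence is limited.** It says that symptoms may occur early, and it directly follows the tacrolimus list. A reader might take it as fixing the timing for both drugs, but it does not clearly cover crisaborole pain.
- **No adverse-event comparison is planned.** Section 11.2 has no between-arm test of adverse events, and section 1.4 has no safety objective. A reader might infer that the main comparison is tilted toward crisaborole. That does not follow: itch and pain interference come from PROMIS questionnaires, which the call script does not alter.
- **Early events are not lost by design.** Volunteered complaints are recorded (9.2), families hold study phone numbers (4.2), the AE Source Doc records interruption or stopping of the drug (5.3), and the Withdrawal Form records time and reason. A reader might infer that early stopping for discomfort would be learned too late to explain. These records contradict that.
- **The size in percentage points is unknown.** The documents give neither reaction rates nor the chance that a named or unnamed symptom is reported. Any figure would rest on invented inputs, and on what share of tacrolimus reactions are burning, since the other three listed are unprompted too.

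All five points stand, and they narrow the concern. They do not remove it: the protocol itself put a burning question beside the general ones, and it gives no reason for treating the other listed reactions differently or for dropping the question after the 6 Week call.

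**Conclusion.** The point holds as a risk in how local reactions are elicited. The script prompts for one of five listed reactions, in two of four calls, and never for the only reaction listed for crisaborole. The first solicited contact follows 14 to 20 of 84 days, on the assumption that Week 3 is Days 15 to 21. Early local reactions therefore depend on recall or volunteered complaints, although section 9.2 places the start of monitoring at the start of treatment.

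The consequence is confined to the descriptive per-arm review in section 9.3 and to any tolerability summary drawn from it. The direction of any distortion rests on the assumption that naming a symptom raises its reporting, which the documents do not address. The change is worth making because it is specific and nearly free.

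**What to change.** 1. In all four calls, replace the burning question (and add it where absent) with one item worded identically for both arms: whether the child has had any pain, burning, stinging, soreness or itching where the ointment was applied, and if so when it started and stopped. Keep the two general questions.
2. Add a resolution date to the AE Source Doc fields in section 5.3, so that they agree with section 9.1.
3. Correct the label of the last reminder call in section 5.1 if it is meant for the 12 Week visit.
4. Reconcile section 9.2 with the call schedule in 5.1, 9.1 and 13. Optionally, existing staff could make one short earlier call using the same item.

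**Cost.** The wording and the extra form field are essentially free. A few more mild events will be recorded. Some will be itch from the disease rather than from the ointment; the attribution field on the AE Source Doc is where that is judged. If the optional call is made, and takes an assumed five minutes for each of up to 48 families, it needs 48 × 5 = 240 minutes, or 4 hours of staff time. The main fix does not depend on it.
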